#### 4.0 DEVICE INFORMATION

4.1 The device being used in this study is the RelieVR by Applied VR . RelievRx by AppliedVR which is an immersive virtual reality device that includes a goggle headset and remote control. The VR experience will be an immersive experience where the child will interact with the system and navigate their way through a game that will involve bright colors, cartoon-like characters, and settings with age-appropriate content.

4.2 Children’s Hospital of Los Angeles has loaned the RelieVR to the study team for short-term use for the purpose of this study.

#### 5.0 SELECTION AND WITHDRAWAL OF SUBJECTS

5.1 Inclusion Criteria: Children meeting the following criteria

- Age 6-17
- ASA I or II
- Present to the Herman Ostrow School of Dentistry Pediatric Dental Clinic and Children’s Dental Health Clinic at Long Beach Memorial Hospital for initial or periodic exam, and are determined to require two or more dental sealants (at least 1 sealant per half mouth)
- The need for nitrous oxide for treatment is not indicated due to cooperative behavior during initial exam. Cooperative behavior is determined through Frankl Score being and F3 or F4.
- Participant and legal guardian must deny any use of nitrous before VR study is presented

5.2 Exclusion Criteria: Children meeting the following criteria:

- Children with visual, auditory, or tactile deficits that would interfere with the ability to complete the experimental tasks
- Children who are unable to tolerate the RelieVR will be screened after consenting to research participation by trying on the VR goggles and stating that they are comfortable and willing to proceed with wearing them during their dental appointment.
- Examples of children who may be unable to tolerate the VR goggles may include:
  - Children who wear glasses and are unable to comfortably adjust the system over their glasses

- Children who experience dizziness, motion sickness or other discomfort during use
  - Patients that score below an F3 on the Frankl scale, indicating uncooperative behavior.
  - Children who remove the VR goggles prior to dental sealant placement
  - Children who present with uncooperative behavior and require pharmacological means to complete dental treatment (nitrous oxide, sedative drugs or general anesthesia)
  - Children with a significant medical history of seizure disorders as flickering from devices can trigger epileptic episodes.
  - Children with developmental disabilities
  - Children with a psychiatric disorder, organic brain syndrome, mental retardation, or other known cognitive/neurological disorders
  - Children that are not English or Spanish speaking
- 5.2.1. If there are any age, ethnic, language, or gender-based exclusion criteria, please provide justification.  
Languages other than English and Spanish will be excluded given that the proposed measures have not been developed nor standardized for use in other languages.
- 5.3 Withdrawal Criteria: The children participating in the study, and their guardians, will be informed that they can withdraw their involvement in the study at any time, and all necessary dental treatment will still be performed at the same level of care.

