## 6.0 STRATIFICATION/DESCRIPTIVE FACTORS/RANDOMIZATION SCHEME

- 6.1 The participants in the study will serve as their own control using a split mouth cross-over randomized control clinical trial design and will be randomly assigned to receive virtual reality or traditional behavior guidance techniques during dental sealant placement. Patients will serve as their own control. Stratification between sites will not be done.
- 6.2 Patient characteristics that will be considered include demographic data such as age, gender, previous dental experience, and number of hours per week the child spends having “screen time”. Additionally, complexity/difficulty of treatment being rendered will be recorded (how many sealants were placed). The dental resident will determine the child’s behavior using the Frankl behavior rating scale at the initial exam, and each subsequent appointment while the child is enrolled in the study.

- 6.3 Randomization will be achieved using an envelope system. Envelopes will be labeled 1 through 52 on the exterior and will serve as the patient's coded study ID. Each envelope will be filled with a single paper slip indicating Group 1, Group 2, Group 3, Group 4. The groups are listed below which takes into account randomization of VR, basic behavioral guidance techniques (BBG), site of mouth. Equal amount of each groups will be represented in the total stack of envelopes. The order of envelopes within the stack will be random. When a child and their parent agree to enroll in the study, an envelope will be drawn from the randomized stack, and the category inside will be assigned to that patient.

	First half of appointment	Second half of appointment
Group 1	VR with right side sealants	BBG with left side sealants
Group 2	VR with left side sealants	BBG with right side sealants
Group 3	BBG with right side sealants	VR with left side sealants
Group 4	BBG with left side sealants	VR with right side sealants

- 6.4 Carryover effect will be reduced by allowing a short rest time between starting the second half of the sealants. For instance, if VR is used first, after finishing sealants on one side of the mouth with VR, the headset will be removed. The patient will then be given 3-5 minutes break before starting the sealants on the second half of the mouth. Carryover effect will also be reduced by randomizing if patients will receive VR for the first half of sealants placed or for the later half.

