#### 10.0 CRITERIA FOR EVALUATION AND ENDPOINT DEFINITIONS

The outcome status (behavior) of all eligible patients will be reported.

Frankl Score: Patient's behavior as rated by the dental provider within one of the following categories: 1= definitely negative, 2= negative, 3= positive, 4= definitely positive. This scale is routinely used by dentists and documented in the patient chart.

Behavior, and anxiety will be scored at the following time points:

- Baseline (patient sitting in the chair prior to treatment)
- During sealant placement with virtual reality distraction
- During sealant placement with basic behavior guidance
- Post Operative (patient sitting upright in chair, 5 minutes post completion of dental sealant placement)

Anxiety: Measured by change in heart rate at outlined points (above) during restorative procedure.

Completion of Dental Treatment: Was the treatment able to be completed, or was the appointment aborted due to patient cooperation, complication with virtual reality system, or any other reason.

Parent Satisfaction Survey: Will be evaluated post treatment for the Virtual Reality and standard of care. Satisfaction questions will be asked on a scale on a scale of 1 to 10. (Appendix A. Figure 3.1 and 3.2)

Healthcare Provider Questionnaire: Will be obtained after each session, completed by the provider performing treatment. (Appendix A. Figure 4)

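### Section 5.2 allows randomized children who do not tolerate VR to be excluded after the envelope is drawn, and Section 10 reports only eligible children

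*Protocol*

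**What the plan says.** **Allocation.** Section 6.3 of the protocol: "When a child and their parent agree to enroll in the study, an envelope will be drawn from the randomized stack". The envelope number is also the study ID (Sections 6.3 and 12). Section 9 places enrollment at the comprehensive or periodic exam. Section 3 describes random assignment as following the scheduling of the sealant appointment.

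**Exclusions.** Section 5.2 says that children "will be screened after consenting to research participation by trying on the VR goggles", with no statement of whether this comes before or after the draw. The same section lists:

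- Headset taken off: "Children who remove the VR goggles prior to dental sealant placement"
- Unwell in VR: "Children who experience dizziness, motion sickness or other discomfort during use"
- Low behavior rating: "Patients that score below an F3 on the Frankl scale, indicating uncooperative behavior"
- Drug support needed: "Children who present with uncooperative behavior and require pharmacological means to complete dental treatment"

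None of the four is limited to the period before allocation.

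**Stopping VR.** Section 7.1 tells families they may stop VR if they wish to withdraw from the study. Section 7.2 gives reasons for taking a child off VR and says nothing about removing the child's data.

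**Reporting.** Section 10: "The outcome status (behavior) of all eligible patients will be reported". The same section defines completion of treatment as an outcome and asks whether treatment was completed or "was the appointment aborted due to patient cooperation, complication with virtual reality system, or any other reason".

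**The concern.** In a within-child comparison, each child drawn from the envelopes should contribute to the result or be visibly accounted for. An exclusion triggered by something that happens under one condition, after allocation, selects children on how that condition went.

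Goggle removal and discomfort in the headset can arise only with VR. Leaving those children out of the reported group hides intolerance, which is one of the main things a pilot of a headset in children should show, and can make VR look better on behavior. A Frankl score below F3 is different: Frankl is the behavior outcome in both halves, so excluding on it after the draw selects on the outcome itself, whichever half produced it.

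The planned analysis is descriptive, mean and range only, in 40 children. A few exclusions can move the mean, and the range is more sensitive still. If the below-F3 rule were applied to ratings at the sealant appointment, the reported Frankl range could only be 3 to 4 on a scale of 1 to 4.

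**Working it through.** The only related figure in the plan is N=40. It is stated without any inputs, so there is nothing to reproduce. The check has two parts: the order of events, and what exclusion could do to the mean difference.

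**1. Order of events**

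| Step | Source | Timing |
|---|---|---|
| Consent and enrollment | Section 9 | Exam visit |
| Envelope drawn | Section 6.3 | At agreement to enroll |
| Envelope drawn (other statement) | Section 3 | After the sealant appointment is scheduled |
| Screen time recorded under the study ID | Sections 3 and 12 | Recruitment; exam-visit note |
| Goggle try-on | Section 5.2 | After consent; order relative to the draw not stated |
| Headset worn for treatment | Section 7.1 | Sealant appointment |

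The two statements on the draw may describe the same moment. On either one, the draw precedes the sealant appointment. The use of the study ID at recruitment supports this, because the ID comes from the envelope. Anything that happens with the headset on at the sealant appointment is therefore after allocation. In Groups 3 and 4 VR comes second, so a VR-triggered exclusion there would follow an already observed half with basic behavior guidance (BBG).

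**2. Effect on the mean paired difference (VR minus BBG)**

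Let f be the share of children removed, D_k the mean difference in those kept and D_r the mean difference in those removed.

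- All children: (1 − f) × D_k + f × D_r
- Kept children only: D_k
- Bias from exclusion: f × (D_k − D_r)

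The protocol gives none of these quantities. Assume D_k = 0, with removed children 1 or 2 Frankl points worse under VR:

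| f | Children of 40 | Bias if D_r = −1 | Bias if D_r = −2 |
|---|---|---|---|
| 5% | 2 | 0.05 × 1 = +0.05 | 0.05 × 2 = +0.10 |
| 10% | 4 | 0.10 × 1 = +0.10 | 0.10 × 2 = +0.20 |
| 20% | 8 | 0.20 × 1 = +0.20 | 0.20 × 2 = +0.40 |

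**3. Does the direction depend on the rule?**

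A simulation of 2,000,000 children gave each a four-level Frankl score in both halves. The underlying scale was the sum of a child component (SD 0.7) and a half-specific component (SD 0.7), cut at −2, −1.2 and 0.2. All of these settings are assumed. Share removed in parentheses:

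| True VR effect (shift on the underlying scale) | All kept | Drop if VR half below F3 | Drop if either half below F3 |
|---|---|---|---|
| None (0) | 0.00 | +0.11 (11%) | 0.00 (19%) |
| Benefit (+0.3) | +0.18 | +0.24 (7%) | +0.12 (15%) |
| Harm (−0.3) | −0.20 | −0.02 (18%) | −0.12 (24%) |

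Dropping VR failures alone moves the result toward VR in every row. Dropping on failure in either half creates no difference where there is none, and shrinks a real one in either direction.

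**4. Do the 52 envelopes show planned replacement?**

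Section 6.3 has 52 envelopes against N=40. The surplus is 12, which is 12/52 = 23.1% of envelopes or 12/40 = 30% of the target. Neither rate is stated, so the surplus is no evidence that excluded children are to be replaced.

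**The case against.** A reader might infer more: that the protocol drops VR failures from the results, that completion is close to 100% by construction, and that every one of these exclusions biases the result toward VR. The documents do not support that, for these reasons.

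- **Try-on reading.** Section 5.2 introduces the goggle criteria through a screening try-on and then gives examples of children who may not tolerate the headset. Discomfort and goggle removal can be read as failures of that try-on. If it came before the draw, the effect would be on generalizability, with no bias in the comparison. This stands as a possible reading. It does not settle the matter, because nothing places the try-on before the draw, and the list as it reads also contains seizure history, developmental disability and language, which are not try-on failures.
- **Entry-criterion reading.** Section 5.1 requires F3 or F4 at the initial exam, and the below-F3 and pharmacological exclusions can be its mirror image. Re-scoring Frankl at later appointments (Section 6.2) is data collection; no passage says a later low score excludes a child. This also stands, but neither exclusion is given a time point.
- **No statement that data are discarded.** Section 7.2 takes a child off VR only, Section 10 counts aborted appointments as an outcome, and Sections 7.1 and 12 have children asked about VR side effects. This defeats the claim that failures are certain to vanish. It also shows the conflict: the same child could be an exclusion under Section 5.2 and an outcome under Section 10.
- **Timing of goggle removal.** A child who takes the goggles off before sealants has no VR-half score at that point, so what is lost first is the intolerance count. The effect on mean Frankl depends on how that child's half is then scored.
- **Left to an SAP.** Analysis populations often are. Eligibility, draw timing and the group whose behavior is reported are fixed in this protocol, so the conflict lies here.

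**Conclusion.** The concern holds in a limited form. The protocol permits headset events to exclude a child after allocation, and its reporting sentence would then allow that child to be left out. For goggle removal and VR discomfort, the possible bias favors VR and intolerance would be under-reported. For the below-F3 and pharmacological criteria, application after the draw would select on the outcome, but the direction is undetermined because failures in the BBG half could be removed too.

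That such exclusions would occur after the draw is an inference from the sequence of steps; the text does not state it. Nor do the documents say that randomized children who fail on VR are dropped. What is certain is that Sections 5.2, 7.2 and 10 cannot all be applied to the same child without a ruling on which governs.

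The size is unknown. The figures of +0.05 to +0.40 Frankl points, and the simulated +0.11 under no effect, rest on assumed rates, score differences and cut points. They show only that a loss of 2 to 8 of 40 children could matter when the report consists of means and ranges.

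**What to change.** 1. Complete the goggle try-on before the envelope is drawn, and state one randomization time in both Section 3 and Section 6.3.
2. Limit Section 5.2 to facts known before the draw, with the Frankl criterion tied to the initial exam, as Section 5.1 already does.
3. In Section 10, make the reported group all randomized patients, as allocated.
4. Report goggle removal, VR discontinuation, side effects and aborted treatment as outcomes by half. Use the observed Frankl score where one was given, and report the number of children without a score. Do not impute the lowest category: a calm child who simply takes off the headset would be rated definitely negative, which builds in a bias against VR.
5. Reconcile Sections 5.2, 7.2 and 10. The clinical handling of these children is unchanged.

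The cost is a protocol amendment to wording and to the order of try-on and draw, with no extra visits or staff. Because the envelope number serves as the study ID at recruitment, the headset must be at hand at the exam visit if the draw stays there. For children already enrolled the order cannot be changed afterward, but each drawn envelope can still be accounted for. A small downside is that the reported VR result may look less favorable.

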## 6.0 STRATIFICATION/DESCRIPTIVE FACTORS/RANDOMIZATION SCHEME

- 6.1 The participants in the study will serve as their own control using a split mouth cross-over randomized control clinical trial design and will be randomly assigned to receive virtual reality or traditional behavior guidance techniques during dental sealant placement. Patients will serve as their own control. Stratification between sites will not be done.
- 6.2 Patient characteristics that will be considered include demographic data such as age, gender, previous dental experience, and number of hours per week the child spends having “screen time”. Additionally, complexity/difficulty of treatment being rendered will be recorded (how many sealants were placed). The dental resident will determine the child’s behavior using the Frankl behavior rating scale at the initial exam, and each subsequent appointment while the child is enrolled in the study.

- 6.3 Randomization will be achieved using an envelope system. Envelopes will be labeled 1 through 52 on the exterior and will serve as the patient's coded study ID. Each envelope will be filled with a single paper slip indicating Group 1, Group 2, Group 3, Group 4. The groups are listed below which takes into account randomization of VR, basic behavioral guidance techniques (BBG), site of mouth. Equal amount of each groups will be represented in the total stack of envelopes. The order of envelopes within the stack will be random. When a child and their parent agree to enroll in the study, an envelope will be drawn from the randomized stack, and the category inside will be assigned to that patient.

	First half of appointment	Second half of appointment
Group 1	VR with right side sealants	BBG with left side sealants
Group 2	VR with left side sealants	BBG with right side sealants
Group 3	BBG with right side sealants	VR with left side sealants
Group 4	BBG with left side sealants	VR with right side sealants

- 6.4 Carryover effect will be reduced by allowing a short rest time between starting the second half of the sealants. For instance, if VR is used first, after finishing sealants on one side of the mouth with VR, the headset will be removed. The patient will then be given 3-5 minutes break before starting the sealants on the second half of the mouth. Carryover effect will also be reduced by randomizing if patients will receive VR for the first half of sealants placed or for the later half.

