### 3.0 STUDY DESIGN

This study is a randomized controlled trial with a crossover design. The study will be carried out at the USC Herman Ostrow School of Dentistry graduate pediatric dental clinic and Children's Dental Health Clinic in Long Beach Memorial Hospital. Patients who are visiting the clinic for a comprehensive or periodic dental exam and are found to require two or more dental sealants (at least one sealant per side) will be recruited for the study. The study subjects will include children ages 6-17 who are ASA I or II (as defined by the American Society of Anesthesiologists classification system). Nitrous oxide for anxiolysis during dental treatment is not indicated for research participants due to signs of cooperative behavior during initial exam. Cooperative behavior is determined through Frankl Score being an F3 or F4. Participant and legal guardian must deny any use of nitrous for dental sealant placement before VR study is introduced and patient is recruited as a prospective participant. The proposed sample size for this pilot study is 40 participants.

This is a split mouth design in which children who are enrolled in the study will serve as both the experimental group and their own control. After the child and parent are scheduled dental sealant appointment, they will be randomly assigned to receive the virtual reality system as a distraction technique for the first half or the latter half of the appointment. During the time where virtual reality is not used, traditional basic behavior guidance techniques will be used, as is the standard of care.

The virtual reality system being used for research purposes is the RelieVR by Applied VR which includes the goggle headset only. The VR experience will be an immersive experience where the child will interact with the system and navigate their way through a game which will involve bright colors, cartoon-like characters and settings with age-appropriate content. The VR system will be worn for approximately 5-10 minutes during sealant application.

Each patient will serve as their own control. The control sample will include basic behavior guidance techniques only. Informed consent will be obtained from the patient or guardian and documented in the patient's record prior to placement of dental sealants and use of virtual reality.

The heart rate will be analyzed at specific steps of the procedure including:

- Baseline (patient sitting in the chair prior to treatment)

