### 1. VR and Frankl Score

Null Hypothesis: There is no difference in Frankl Score between a visit where virtual reality is used and a visit where basic behavior guidance is used during dental sealant placement.

Alternative Hypothesis: Frankl score will improve when virtual reality distraction is used during dental sealant placement.

Sample Size: N=40

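### Section 6.3 secures equal order-by-side groups only over all 52 envelopes, but 40 children are planned and the 12 extra envelopes are unexplained

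*Protocol*

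**What the plan says.** Section 6.3 describes the randomisation: "Envelopes will be labeled 1 through 52 on the exterior and will serve as the patient's coded study ID". On content it says "Each envelope will be filled with a single paper slip indicating Group 1, Group 2, Group 3, Group 4". The groups cross the order of the two conditions (VR first or basic behavior guidance first) with the side of the mouth treated first. On balance it says "Equal amount of each groups will be represented in the total stack of envelopes", and on sequence "The order of envelopes within the stack will be random". No blocks are mentioned. On use it says "When a child and their parent agree to enroll in the study, an envelope will be drawn from the randomized stack". Section 6.1 adds "Stratification between sites will not be done".

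The sample size is given twice, and the two statements agree. Section 3.0 has "The proposed sample size for this pilot study is 40 participants", and Section 13, under the Frankl score hypothesis, has "Sample Size: N=40".

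Sections 3.0 and 13.1 limit the analysis to means and ranges. Section 3.0 also lists the half of the appointment in which VR is given among the factors to be looked at. Section 6.4 relies on the randomised order as one of two safeguards against carryover.

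**The concern.** The only balance that the scheme guarantees is over the full stack. With the envelopes in simple random order, the 40 that are used are a random subset of the 52, and nothing makes that subset balanced. The protocol gives no loss allowance, replacement rule or over-enrolment figure that would connect 52 with 40.

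At stake is the balance of order and side. Each child is their own control, so the numbers in the four groups do not affect comparability between children. They do decide how far a difference between the first and second half of the appointment (settling in, fatigue, familiarity) cancels out of the mean VR-minus-guidance difference. With only means and ranges planned, balance by design is the main protection against that.

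**Working it through.** **Inputs.** 52 envelopes, four groups, equal numbers and random order (Section 6.3); 40 children (Sections 3.0 and 13). The protocol gives no basis for the 40, so there is no derivation to reproduce. The stack is consistent in itself: 52/4 = 13 per group.

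**Could 52 be 40 plus an allowance for loss?** 40/(1 − d) = 52 gives d = 1 − 40/52 = 23.1%. Equivalently, 52 = 40 × 1.3. Neither rate appears in the protocol.

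**Four groups equal at 40.** When 40 envelopes are used out of 4 × 13 in random order, the counts are multivariate hypergeometric:

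P(10/10/10/10) = C(13,10)^4 / C(52,40) = 286^4 / C(52,40) = 0.0324, or 3.2%.

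Enumerating all possible splits, the largest and smallest groups differ by 4 or more with probability 37%. The expected gap is 3.1.

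**Order split.** Let k be the number of VR-first children. It is hypergeometric (52 envelopes, 26 VR-first, 40 used), with mean 20 and SD = √(40 × 0.25 × 12/51) = 1.53.

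| Split, in either direction | Probability |
|---|---|
| exactly 20/20 | 25.7% |
| 22/18 or worse | 1 − 0.2568 − 2 × 0.2097 = 32.4% |
| 23/17 or worse | 1 − 0.9025 = 9.7% |

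The side on which VR is used follows the same distribution, because it too divides the stack 26/26.

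**Effect on a crude mean.** Let τ be the VR effect and π the second-half-minus-first-half effect. A VR-first child has expected difference τ − π, and a guidance-first child τ + π. The mean over 40 children is

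τ + π(40 − 2k)/40.

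The share of π left in is |40 − 2k|/40:
- at 22/18, 4/40 = 10%
- at 23/17, 6/40 = 15%
- on average, E|k − 20| = 2 × (1 × 0.2097 + 2 × 0.1132 + 3 × 0.0394 + 4 × 0.0084 + 5 × 0.0010 + 6 × 0.00005) = 1.19, and 2 × 1.19/40 = 5.9%

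The protocol gives no value for π. If it were 5 beats per minute, which is purely an assumption, the average residue would be about 0.3 and the residue at 22/18 would be 0.5 beats per minute. Both scale in proportion to π.

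**Averaging by order.** The equal-weight average of the two order-specific means is [(τ − π) + (τ + π)]/2 = τ for any k. Its efficiency relative to a 20/20 split is 4k(40 − k)/1600: 0.99 at 22/18, 0.9775 at 23/17, and 0.994 on average.

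**After the repair.** With permuted blocks that have a boundary at 40, the first 40 allocated are 10/10/10/10, hence 20/20 by order, with certainty. At any other stopping point the groups differ by at most 1 within a block of 4 and at most 2 within a block of 8.

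**The case against.** The strongest reply is that nothing promised is broken. Section 6.3 claims equality over the total stack, which holds, and nowhere promises 10 per group at 40. Spare envelopes are ordinary practice. The protocol also suggests a use for them: the envelope is drawn at agreement to enrol, while Section 5.2 screens goggle tolerance after consent and Section 5.3 allows withdrawal at any time. Some envelopes may therefore go to children who yield no data. This reading is reasonable, but it is an inference, since no loss rate or replacement rule is stated. It also does not restore balance: if all 52 were drawn and 12 children lost at random, the remaining 40 would again be equal only 3.2% of the time.

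The harm is also small. Order is randomised, so the expected bias is zero. The restricted stack already does better than simple randomisation, under which exact equality at 40 has probability 0.4%. Section 3.0 foresees looking at VR timing, so results by order are within reach of the plan. All of this stands, and it limits the size of the point.

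Two stronger readings are tempting and are not supported. A reader might infer that the sections disagree on the size of the trial. They do not: Sections 3.0 and 13 both say 40, and Section 6.3 counts only envelopes. A reader might also infer that drawing from the stack, rather than working through the numbers, worsens balance. It does not: any draw made without knowledge of the contents from a randomly ordered stack has the same distribution as taking the envelopes in number order.

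**Conclusion.** The point holds as a modest design weakness. Equal groups are fixed at 52, a number that the protocol does not plan to enrol, and the difference from 40 is unexplained. At 40 used envelopes, exact equality has a 3.2% chance and an order split of 22/18 or worse a 32% chance. The consequence is chance imbalance that leaves on average about 6% of any period effect in a crude mean; it is not systematic bias. The figures assume that exactly 40 envelopes are used, or that 40 children remain after random losses, and that the stack is in simple random order as written. If all 52 were enrolled and analysed, the groups would be 13 each and the point would fall away, but the protocol does not say so. It is worth acting on because only means and ranges are planned and the repair costs almost nothing.

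**What to change.** 1. State in Section 6.3 that 40 children are planned and that the 12 further envelopes are spares, for example to replace children lost after the draw. If they serve another purpose, state that instead.
2. Fill the 52 envelopes in one concealed sequence of permuted blocks over Groups 1 to 4, of size 4 with some of 8 and a block boundary at 40. Use them strictly in number order. The first 40 allocated are then 10 per group. This needs no stratification by site and leaves that choice in Section 6.1 as it is.
3. Blocks balance the children allocated, not those left after later losses. Therefore also report the VR-minus-guidance mean separately for VR-first and guidance-first children, and average the two with equal weight. This removes the period effect whatever the split and stays within the planned descriptive analysis.

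The cost is refilling the envelopes before the first child, a paragraph of text and one extra pair of means. Number order across two clinics also requires someone to keep the running number. If enrolment has begun, the explanation and the reporting by order still apply, and the unused envelopes can still be blocked. The one downside is a slightly more predictable allocation. Mixed block sizes reduce it, and it matters little because every child receives both conditions.
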